6.3.3 Criteria for LDK378 dose modifications

LDK378 dose reduction will follow the dose reduction steps described in [Table 6-2](#). For each patient, a maximum of 3 dose modifications is allowed after which the patient must be discontinued from treatment with LDK378. Once the dose of LDK378 has been reduced, it cannot be re-escalated. If a patient continues treatment with LDK378 after RECIST-defined PD as determined by the investigator, the criteria for dose modification will also apply.

Table 6-2 Dose reduction steps for LDK378

LDK378 dose levels	Dose* and schedule
Starting dose level	750 mg qd continuously
Dose level – 1	600 mg qd continuously
Dose level – 2	450 mg qd continuously
Dose level – 3	300 mg qd continuously **

*Dose reduction should be based on the worst preceding toxicity as per NCI-CTCAE version 4.03.

**Dose reduction below 300 mg/day is not allowed. If a dose reduction below 300 mg/day is required, the patient should be permanently discontinued from LDK378

Guidelines for dose interruptions and re-initiation of LDK378 treatment (with or without dose reduction) are described in [Table 6-3](#).

Table 6-3 Criteria for interruption and re-initiation of LDK378 treatment

Worst toxicity (CTCAE 4.03 Grade)*	Dose Modifications for LDK378
HEMATOLOGICAL	
Neutropenia (ANC: Absolute neutrophil count)	
Grade 1 (ANC < LLN - $1.5 \times 10^9/L$)	Maintain dose level
Grade 2 (ANC < 1.5 and $\geq 1.0 \times 10^9/L$)	
Grade 3 (ANC < 1.0 and $\geq 0.5 \times 10^9/L$)	
Grade 4 (ANC < $0.5 \times 10^9/L$)	Omit dose until resolved to \leq Grade 2, then: If resolved in \leq 7 days, then maintain dose level If resolved in $>$ 7 days, then \downarrow 1 dose level
Febrile neutropenia (ANC < $1.0 \times 10^9/L$, with a single temperature of $\geq 38.3^{\circ}C$ or a sustained temperature of $\geq 38^{\circ}C$ for more than one hour)	Omit dose until clinically resolved and neutropenia \leq Grade 2, then \downarrow 1 dose level
Thrombocytopenia	
Grade 1 (PLT < LLN - $75 \times 10^9/L$)	Maintain dose level
Grade 2 (PLT < 75 and $\geq 50 \times 10^9/L$)	
Grade 3 (PLT < 50 and $\geq 25 \times 10^9/L$)	Omit dose until resolved to \leq Grade 2, then: If resolved in \leq 7 days, then maintain dose level If resolved in $>$ 7 days, then \downarrow 1 dose level
Grade 4 (PLT < $25 \times 10^9/L$)	Omit dose until resolved to \leq Grade 2, then \downarrow 1 dose level
HEPATIC	
Alkaline phosphatase and/or Gamma-glutamyl transpeptidase (GGT)	
Isolated elevations of any grade	Maintain dose level
Total Bilirubin** (for patients with Gilbert Syndrome these dose modifications apply to changes in direct [conjugated] bilirubin only)	
Grade 1 ($>$ ULN and $\leq 1.5 \times$ ULN)	Maintain dose level with liver function test (LFTs)*** monitored as per protocol

Worst toxicity (CTCAE 4.03 Grade)*	Dose Modifications for LDK378
Grade 2 (> 1.5 and \leq 3.0 x ULN) with ALT or AST \leq 3.0 x ULN	Omit dose until resolved to \leq Grade 1, then: If resolved in \leq 7 days, then maintain dose level If resolved in > 7 days, then \downarrow 1 dose level
Grade 3 (> 3.0 and \leq 10.0 x ULN) with ALT or AST \leq 3.0 x ULN	Omit dose until resolved to \leq Grade 1, then: If resolved in \leq 7 days, \downarrow 1 dose level If resolved in > 7 days discontinue patient from LDK378
Grade 4 (> 10.0 x ULN)	Permanently discontinue patient from LDK378
AST or ALT	
Grade 1 (> ULN and \leq 3.0 x ULN)	Maintain dose level with LFTs*** monitored per protocol
Grade 2 (> 3.0 and \leq 5.0 x ULN) without total bilirubin elevation to > 2.0 x ULN	Maintain dose level with LFTs*** monitored per protocol
Grade 3 (> 5.0 and \leq 20.0 x ULN) without total bilirubin elevation to > 2.0 x ULN	Omit dose until resolved to \leq Grade 1, then \downarrow 1 dose level
Grade 4 (> 20.0 x ULN) without total bilirubin elevation to > 2.0 x ULN	Omit dose until resolved to \leq Grade 1, then \downarrow 1 dose level
AST or ALT and concurrent total bilirubin	
AST or ALT > 3.0 x ULN with total bilirubin > 2.0 x ULN in the absence of cholestasis or hemolysis	Permanently discontinue patient from LDK378 Refer to Section 6.3.4.2 for additional follow-up
PANCREATIC	
Amylase and/or lipase elevations (in the absence of clinical symptoms)	
Grade 1 (> ULN and \leq 1.5 x ULN)	Maintain dose level
Grade 2 (> 1.5 - 2.0 x ULN)	Maintain dose level
Grade \geq 3 (> 2.0 x ULN)	Omit dose until resolved to \leq Grade 1, then \downarrow 1 dose level
Note: Withhold LDK378 for acute onset of new or progressive unexplained abdominal symptoms, such as severe pain or vomiting; perform diagnostic procedures (e.g., abdominal CT scan or ultrasound) to exclude pancreatic pathology.	

Worst toxicity (CTCAE 4.03 Grade)*	Dose Modifications for LDK378
RENAL	
Serum creatinine	
Grade 1 (>1 and ≤ 1.5 x baseline; > ULN and ≤1.5 x ULN)	Maintain dose level
Grade 2 (> 1.5 and ≤ 3 x baseline; >1.5 and ≤3.0 x ULN)	Omit dose until resolved to ≤ Grade 1, then: If resolved in ≤ 7 days, then maintain dose level If resolved in > 7 days, then ↓ 1 dose level
Grade 3 (> 3.0 x baseline ; >3.0 and ≤6.0 x ULN)	Omit dose until resolved to ≤ Grade 1, then ↓ 1 dose level
Grade 4 (> 6.0 x ULN)	Permanently discontinue patient from LDK378
GASTROINTESTINAL	
Diarrhea****	
Grade 1	Maintain dose level but adjust anti-diarrhea treatment
Grade 2 (despite maximal anti-diarrheal medication)	Omit dose until resolved to ≤ Grade 1, then maintain dose level. If diarrhea returns as ≥ Grade 2, then omit dose until resolved to ≤ Grade 1, then ↓ 1 dose level
Grade 3 (despite maximal anti-diarrheal medication)	Omit dose until resolved to ≤ Grade 1, then ↓ 1 dose level
Grade 4 (despite maximal anti-diarrheal medication)	Omit dose until resolved to ≤ Grade 1, then ↓ 1 dose level
Nausea*****	
Grade 1 or 2	Maintain dose level but adjust anti-emetic treatment
Grade 3 (despite standard anti-emetics)	Omit dose until resolved to ≤ Grade 1, then ↓ 1 dose level
Vomiting*****	
Grade 1	Maintain dose level but adjust anti-emetic treatment
Grade 2 (despite standard anti-emetics)	Omit dose until resolved to ≤ Grade 1, then maintain dose level. If vomiting returns as ≥ Grade 2, then suspend dose until resolved to ≤ Grade 1, then ↓ 1 dose level.
Grade 3 (despite standard anti-emetics)	Omit dose until resolved to ≤ Grade 1, then ↓ 1 dose level
Grade 4 (despite standard anti-emetics)	Omit dose until resolved to ≤ Grade 1, then ↓ 1 dose level

Worst toxicity (CTCAE 4.03 Grade)*	Dose Modifications for LDK378
METABOLIC	
Any Grade hypophosphatemia	Treatment with phosphate supplements as clinically indicated and maintain dose level
Persistent hyperglycemia (glucose > 250 mg/dL) despite optimal anti-hyperglycemic therapy	Omit dose until hyperglycemia is adequately controlled then resume LDK378 at ↓ 1 dose level If adequate hyperglycemic control cannot be achieved with optimal medical management permanently discontinue patient from LDK378
GENERAL DISORDERS	
Fatigue (asthenia)	
Grade 1 or 2	Maintain dose level
Grade 3	If grade 3 fatigue resolves to Grade 2 in ≤ 7 days, maintain dose level If grade 3 fatigue lasts > 7 days, omit dose until resolved to ≤ Grade 2 and then ↓ dose level
PULMONARY	
Notes:	

Withhold LDK378 for acute onset of new or progressive unexplained pulmonary symptoms, such as dyspnea, cough and fever and during diagnostic workup for pneumonitis/ILD.During evaluation of potential grade 2, 3, and 4 pneumonitis, if an infectious etiology is confirmed (i.e., pneumonia) and pneumonitis is excluded, then consider resuming LDK378 at current dose level after the pneumonia resolves.	
PNEUMONITIS	
Any Grade treatment-related ILD/pneumonitis	Permanently discontinue patient from LDK378
CARDIAC	
Electrocardiogram QT corrected (QTcF) interval prolonged	
Grade 1 (QTcF 450-480 ms)	Maintain dose level
Grade 2 (QTcF 481-500 ms)	

Worst toxicity (CTCAE 4.03 Grade)*	Dose Modifications for LDK378
Grade 3 (QTcF \geq 501 ms on at least two separate ECGs)	
Omit dose until QTc is less than < 481 ms, then \downarrow 1 dose level
 
- Assess the quality of the ECG recording and the QT value and repeat if needed- Repeat ECG in 24 hours, or less, as clinically indicated; continue monitoring as clinically indicated until QTc < 481 ms 
In addition:-Determine the serum electrolyte levels (in particular hypokalemia, hypomagnesemia). If abnormal, correct abnormalities before resuming study drug treatment
 
- Review concomitant medication use for drugs with the potential to increase the risk of drug exposure related to QT prolongation 
After resumption of dosing:
 
- Repeat ECGs 7 days after dose resumption for all patients who had therapy interrupted due to QTc ≥ 501 ms.
Grade 4 (QTcF ≥ 501 or > 60 ms change from baseline and Torsades de pointes or polymorphic ventricular tachycardia or signs/symptoms of serious arrhythmia)	Permanently discontinue patient from LDK378
BRADYCARDIA	
Grade 1 or Grade 2	
Omit dose until recovery to asymptomatic bradycardia or to a heart rate ≥ 60 bpm
 
Evaluate concomitant medications known to cause bradycardia and adjust the dose of LDK378

Grade 3 Grade 4 (in patients taking a concomitant medication also known to cause bradycardia or a medication known to cause hypotension)	
Omit dose until recovery to asymptomatic bradycardia or to a heart rate ≥ 60 bpm
 
If the concomitant medication can be adjusted or discontinued, resume LDK378 at \downarrow 1 dose level with frequent monitoring

Grade 4 (in patients who are not taking a concomitant medication also known to cause bradycardia or known to cause hypotension)	Permanently discontinue patient from LDK378

Worst toxicity (CTCAE 4.03 Grade)*	Dose Modifications for LDK378
* Common Terminology Criteria for Adverse Events (CTCAE) version 4.03. All dose modifications should be based on the worst preceding toxicity.	
** If Grade 3 or 4 hyperbilirubinemia is due to the indirect (non-conjugated) component only, and hemolysis as the etiology has been ruled out as per institutional guidelines (e.g., review of peripheral blood smear and haptoglobin determination), then ↓ 1 dose level and continue treatment at the discretion of the Investigator.	
***LFTs include albumin, ALT, AST, total bilirubin, alkaline phosphatase and GGT.	
**** Dose modifications apply to patients who experience diarrhea despite appropriate antidiarrheal medication. This medication should be started at the first sign of abdominal cramping, loose stools or overt diarrhea (see Section 6.3.4.6).	
***** Dose modifications apply to patients who experience nausea and/or vomiting despite appropriate antiemetic medication. This medication should be started at the first sign of nausea and/or vomiting (see Section 6.3.4.5).	

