6.3 Dose modifications

6.3.1 Dose modification and dose delay

For patients who do not tolerate the protocol-specified dosing schedule, dose adjustments are permitted in order to allow the patients to continue the study treatment. Any changes in LDK378 must be recorded on the Dosage Administration Record eCRF.

General guidelines for dose modifications for toxicities other than those listed in [Table 6-3](#).

For grade 1 and tolerable grade 2 treatment-related toxicities, patients are encouraged to continue at the current dose of study treatment. For intolerable grade 2 treatment-related toxicities, dosing should be interrupted until resolution to grade 1 or lower followed by dose reduction to the next dose level. For grade 3 or grade 4 treatment-related toxicity that is not considered by the investigator to be life-threatening, patients should interrupt study treatment until resolution to grade 1 or lower; then study treatment may continue following a dose reduction to the next dose level, if in the opinion of the Investigator, the patient continues to experience clinical benefit and after discussion with the Sponsor. For any grade 3 or 4 treatment-related toxicity that is considered by the investigator to be life-threatening, permanently discontinue study treatment.

More detailed LDK378 modification guidelines are described in [Section 6.3.3](#) and [Table 6-3](#) selected toxicities.

All dose modifications, interruptions or discontinuations must be based on the worst preceding toxicity as graded by the NCI Clinical Toxicity Criteria (NCI-CTCAE) version 4.03. Patients whose treatment is interrupted or permanently discontinued due to an AE must be followed until resolution or stabilization of the event. Patients requiring interruptions greater than 28 consecutive days will be discontinued from study treatment. In certain cases, if the Investigator and the Sponsor conclude that a patient, who has experienced a treatment interruption greater than 28 consecutive days, could benefit from additional treatment, continuation may be allowed.

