6.3.2 Treatment interruption and treatment discontinuation

If the administration of LDK378 is temporarily interrupted for reasons other than toxicity, then treatment with LDK378 may be resumed at the same dose. The same applies if the patient experiences an unacceptable toxicity not specifically described in [Table 6-3](#), provided this toxicity resolved to \leq CTCAE grade 1.

If the treatment with LDK378 is withheld due to toxicity, scheduled visits and all assessments should continue to be performed (with the exception of the dosing of the withheld study drug), as described in [Table 7-1](#).

If the treatment with LDK378 dosing is withheld for more than 28 consecutive days (counting from the first day when a dose was missed), due to treatment-related toxicity, then LDK378 should be permanently discontinued except in cases where the investigator believes the patient continues to derive clinical benefit. In such cases, treatment with LDK378 may be resumed at a lower dose.

Detailed guidelines for follow-up of study drug related AE or an abnormal laboratory value must be followed as described in [Section 6.3.4](#).

All patients will be followed for safety until 30 days after the last dose of LDK378. Patients whose treatment is temporarily interrupted or permanently discontinued due to an AE or abnormal laboratory value must be followed until resolution or stabilization of the event, whichever comes first, including all study assessments appropriate to monitor the event.

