- For patients with elevated AST or ALT or TBIL value at baseline: [AST or ALT > 2 x baseline AND > 3.0 x ULN] OR [AST or ALT > 8.0 x ULN], combined with [TBIL > 2 x baseline AND > 2.0 x ULN]
- Medical review needs to ensure that liver test elevations are not caused by cholestasis, defined as: ALP elevation > 2.0 x ULN with R value (ALT/ALP in x ULN) < 2 in patients without bone metastasis, or elevation of ALP liver fraction in patients with bone metastasis.
- Note: (The R value is calculated by dividing the ALT by the ALP, using multiples of the ULN for both values. It denotes the relative pattern of ALT and/or ALP elevation is due to cholestatic or hepatocellular liver injury).
- In the absence of cholestasis, these patients should be immediately discontinued from study drug treatment, and repeat LFT testing as soon as possible, preferably within 48 hours from the awareness of the abnormal results. The evaluation should include laboratory tests, detailed history, physical assessment and the possibility of liver metastasis or new liver lesions, obstructions/compressions, etc.
 - Laboratory tests should include ALT, AST, albumin, creatinine kinase, total bilirubin, direct and indirect bilirubin, GGT, prothrombin time (PT)/INR and alkaline phosphatase.
 - A detailed history, including relevant information, such as review of ethanol, concomitant medications, herbal remedies, supplement consumption, history of any pre-existing liver conditions or risk factors, should be collected.
 - Further testing for acute hepatitis A, B, C or E infection and liver imaging (eg, biliary tract) may be warranted.
 - Blood sample can be collected as close as possible to last dose of study drug in the event that a patient experiences hepatotoxicity, as needed.
 - Additional testing for other hepatotropic viral infection (CMV, EBV or HSV), autoimmune hepatitis or liver biopsy may be considered as clinically indicated or after consultation with specialist/hepatologist.

All cases confirmed on repeat testing meeting the laboratory criteria defined above, with no other alternative cause for LFT abnormalities identified should be considered as “medically significant”, thus, met the definition of SAE ([Section 8.2.1](#)) and reported as SAE using the term “potential drug-induced liver injury”. All events should be followed up with the outcome clearly documented.

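### Table 6-3 holds LDK378 for bilirubin >1.5 to 2.0 x ULN with normal transaminases but maintains the dose when ALT and AST are both >3 to 5 x ULN, and has no row for higher bilirubin with both raised and cholestasis

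*Protocol*

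**What the plan says.** All of this is in the hepatic part of Protocol Table 6-3 (Section 6.3.3) and in Section 6.3.4.2.

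- **Bilirubin Grade 2** (>1.5 to 3.0 x ULN): omit the dose until Grade 1 or lower, then resume at the same dose if resolved within 7 days, otherwise one level lower. The row is restricted: "3.0 x ULN) with ALT or AST" at or below 3.0 x ULN. **Grade 3** (>3.0 to 10.0) carries the same restriction; the patient resumes one level lower if resolved within 7 days and otherwise stops. **Grade 4** (>10.0) is a permanent stop without a transaminase condition.
- **AST or ALT Grade 2** (>3.0 to 5.0 x ULN): maintain the dose, restricted by "5.0 x ULN) without total bilirubin elevation to > 2.0 x ULN". Grades 3 and 4 carry the same bilirubin restriction; the dose is omitted and then reduced one level.
- **Combined row**, permanent stop: "AST or ALT > 3.0 x ULN with total bilirubin > 2.0 x ULN in the absence of cholestasis or hemolysis".
- **Section 6.3.4.2** has its own stop: "In the absence of cholestasis, these patients should be immediately discontinued from study drug treatment". It does not exempt hemolysis. When baseline values are raised, its transaminase threshold is "AST or ALT > 2 x baseline AND > 3.0 x ULN] OR [AST or ALT > 8.0 x ULN", combined with bilirubin above both 2 x baseline and 2.0 x ULN. It defines cholestasis as "ALP elevation > 2.0 x ULN with R value (ALT/ALP in x ULN) < 2 in patients without bone metastasis", or a raised liver fraction of ALP in patients with bone metastasis.
- **Section 6.3.1** introduces its rules as "General guidelines for dose modifications for toxicities other than those listed in" Table 6-3. **Section 6.3.2** allows resumption at the same dose after interruption for reasons other than toxicity, and adds: "The same applies if the patient experiences an unacceptable toxicity not specifically described in" Table 6-3, once resolved to Grade 1 or lower.

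**The concern.** A dose-modification table should never give a milder instruction as the picture worsens, and every combination of values should lead to some instruction. Here the bilirubin rows drop out once both transaminases pass 3.0 x ULN, but the combined row does not take over until bilirubin passes 2.0 x ULN. Between 1.5 and 2.0 only the transaminase row is left, and at Grade 2 it says to maintain. Above 2.0, the combined row switches off with cholestasis or hemolysis, the transaminase rows are already off, and the bilirubin rows are off as well.

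What is at stake is patient safety and consistent dosing between sites. Hepatotoxicity is an adverse event of special interest (Section 8.1.3), and Section 12 allows no authorized deviations, so sites are expected to follow the table. Patients with liver metastases may enter with ALT and AST up to 5 x ULN (Section 5.2, criterion 10), so a rise in bilirubin alone can put them in the inverted region.

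**Working it through.** The plan gives no figure to reproduce, so the check is of rule logic. The restriction to ALT or AST at or below 3.0 x ULN can mean either one or both. Cases with ALT and AST both above 3.0 give the same answer under both readings.

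**Single cases (multiples of ULN)**

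| ALT | AST | Bilirubin | Cholestasis | Row met | Action |
|---|---|---|---|---|---|
| normal | normal | 1.8 | no | Bilirubin Grade 2 | omit |
| 4 | 4 | 1.8 | no | AST/ALT Grade 2 | maintain |
| 6 | 6 | 1.8 | no | AST/ALT Grade 3 | omit, then reduce |
| 4 | 4 | 2.5 | no | Combined | permanent stop |
| 4 | 4 | 2.5 | yes (ALP 3, R = 4/3 = 1.33) | none | none; 6.3.4.2 also gives no action |

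The first two rows are the inversion. The rule of acting on the worst preceding toxicity does not resolve it, because bilirubin 1.8 and ALT 4 are both Grade 2. The third row shows how narrow it is: above 5 x ULN the dose is held again.

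**Grid.** ALT and AST each take the values 1, 2, 3, 3.5, 4, 5, 6, 10, 20, 25. Bilirubin takes 1, 1.2, 1.5, 1.6, 1.8, 2, 2.1, 2.5, 3, 3.5, 5, 10, 12. The counts are table cells, not patients.

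- Inversion, either-one reading: both transaminases in {3.5, 4, 5} gives 3 x 3 = 9 pairs; times 3 bilirubin values (1.6, 1.8, 2) = 27 cells. Both-must-be-low reading: the higher value in {3.5, 4, 5} gives 36 - 9 = 27 pairs; times 3 = 81 cells.
- No row with cholestasis, either-one reading: both above 3 gives 7 x 7 = 49 pairs; times 6 bilirubin values (2.1 to 10) = 294. Both-must-be-low reading: 100 - 9 = 91 pairs; times 6 = 546.
- Of those, Grade 2 throughout (bilirubin at most 3, transaminases at most 5): 9 x 3 = 27, or 27 x 3 = 81. The rest, 294 - 27 = 267 or 546 - 81 = 465, include a Grade 3 or 4 value.
- Without cholestasis or hemolysis, no cell lacks a row.

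**Hemolysis and raised baseline**

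- Hemolysis, normal baseline, bilirubin >2 to 10 with a transaminase above 3: the combined row does not apply but 6.3.4.2 stops the drug (91 x 6 = 546 cells).
- Baseline ALT and AST 4.5, bilirubin 1, neither cholestasis nor hemolysis: the table stops at bilirubin >2 with a transaminase >3, while 6.3.4.2 needs more than 2 x 4.5 = 9 or more than 8 x ULN. The higher transaminase lies above 3 and at or below 8 in 49 - 9 = 40 pairs; times 6 = 240 cells.
- Hemolysis together with that baseline, both transaminases in {3.5, 4, 5, 6}: 16 x 6 = 96 cells (240 if both must be low) with neither a row nor a 6.3.4.2 stop.

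**Frequency (Table 1-1, N = 255).** Grade 3-4 ALT increase 76/255 = 29.8%, or 5.96 in 20; Grade 3-4 AST increase 25/255 = 9.8%, or 1.96 in 20; any-grade ALP increase 45/255 = 17.6%, or 3.53 in 20. No bilirubin term reaches the table's 10% threshold, so each was at most 25/255, fewer than 2 in 20.

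**The case against.** The strongest reply concerns the cholestasis gap. A reader might infer that the protocol has no hold rule there, and the documents do not support that. If a combination that matches no row counts as a toxicity not listed in Table 6-3, Section 6.3.1 applies: for treatment-related Grade 3-4 toxicity it interrupts until Grade 1 or lower and resumes only at a reduced dose after discussion with the sponsor, or stops the drug if the toxicity is life-threatening. That reaches 267 of 294 (or 465 of 546) gap cells when the event is treatment-related. Whether 6.3.1 applies is arguable, because ALT, AST and bilirubin are all listed in the table. If it does, the remaining Grade 2 cells are still encouraged to continue at the current dose when tolerable; ALT 4, AST 4, bilirubin 2.5 is one. Section 6.3.2, the other candidate, sets no hold of its own.

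A reader might also infer that table and text conflict dangerously on hemolysis and raised baselines. No sentence says to continue in those cases. The table's hemolysis exemption limits one row, and the baseline-adjusted criteria in 6.3.4.2 define who needs further follow-up. Read together, the two give a stop except when hemolysis and a raised baseline coincide and the 6.3.4.2 thresholds are not met.

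Monitoring also limits the harm: LFTs are at least weekly from Grade 2 (Section 6.3.4.2), and the investigator should stop treatment judged detrimental (Section 7.1.3). These safeguards stand, but they do not correct the written dosing instruction.

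**Conclusion.** Two defects hold under both readings of the transaminase condition. The inversion is certain from the table alone but narrow: bilirubin >1.5 to 2.0 x ULN with ALT and AST both >3 to 5 x ULN. The missing row for cholestasis is also certain, but its consequence depends on whether Section 6.3.1 applies; even if it does, tolerable Grade 2 combinations stay on full dose. The differences on hemolysis and raised baselines are a harmonisation point for the sponsor, not a demonstrated safety error.

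Few of about 20 patients are likely to be affected. The documents do not give the share, bilirubin elevation is the limiting component, and adverse-event terms can miss laboratory-only values. The ORR analysis is unchanged. The table should be corrected because it governs dosing for a known toxicity of the drug.

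The check leaves out Gilbert syndrome, where only direct bilirubin counts, and the double-asterisk footnote, which reduces the dose one level for Grade 3-4 bilirubin that is indirect only with hemolysis ruled out.

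**What to change.** 1. Delete the transaminase condition from the bilirubin Grade 2 and 3 rows.
2. Delete the bilirubin condition from the AST/ALT Grade 2, 3 and 4 rows.
3. Keep the combined discontinuation row.
4. Add: when more than one hepatic row applies, the most restrictive governs.
5. State one hemolysis rule and one baseline rule, identically in Table 6-3 and Section 6.3.4.2. The choice is the sponsor's. The default that loosens no current stop is to keep the stop: fixed thresholds and no hemolysis exemption. Every case that 6.3.4.2 stops already exceeds 3.0 x ULN and bilirubin 2.0 x ULN, so that row covers them all. Exempting hemolysis in both places would turn the 546 text-mandated stop cells into holds; adopting the baseline-adjusted thresholds would do the same for the 240 baseline cells.

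On the grid, these edits leave no combination without a row and none treated more mildly than a less abnormal one. The sponsor should confirm how the double-asterisk footnote sits with item 4.

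The cost is a written amendment with IRB/IEC approval and, where required, health authority approval (Section 12.1). No tests, staff or patients are added. Expect a few more dose holds, and some discontinuations when Grade 3 bilirubin with raised transaminases and cholestasis does not resolve within 7 days (49 x 3 = 147 or 91 x 3 = 273 of the gap cells carry Grade 3 bilirubin). Keeping the stop also adds one in the rare case of hemolysis with a raised baseline that is now without instruction.
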